#### Secondary study endpoints

- 1) Lymph node dissection: Record the total number of lymph node dissection, the number of stations of lymph node dissection, and the number of lymph node dissection at each station during the operation, and evaluate them according to the pathologic results.
- 2) Perioperative indicators: Record the duration of surgery, intraoperative bleeding, the incidence of intraoperative accidents, evaluated by surgical records and perioperative clinical manifestations, laboratory tests, physical examination;
- 3) Postoperative short-term efficacy indicators: record the length of postoperative hospitalization (days), survival within 30 days after surgery, and evaluate through postoperative follow-up;
- 4) Perioperative complication rate: Evaluated by clinical manifestations, laboratory tests, and physical examination.
- 5) 3-year disease-free survival rate: defined as the proportion of patients without tumor recurrence or metastasis 3 years after surgery, evaluated by postoperative follow-up.
- 6) 3-year overall survival rate: defined as the proportion of patients who are still alive 3 years after surgery, and evaluated by postoperative follow-up.

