### 2.2 Background

For operable early lung cancer, sub-lobe resection has been demonstrated to achieve similar oncologic outcomes compared with lobectomy [2, 3], while preserving the lung function. Pneumonectomy remains the standard surgical procedure for patients whose surgical strategies are pneumonectomy initially, although tumor downstaging after neoadjuvant therapy. More evidence is needed to determine whether the extent of surgical resection can be reduced for these patients.

Although pneumonectomy ensures a good R0 clearance rate, it is associated with a higher rate of perioperative complications and mortality than lobectomy. 355 patients with pneumonectomy were retrospectively analyzed by Gregory D. Jones' team [4], and the mortality rates were 3.7%, 4.5%, and 6.8% at in-hospital, 30 days, and 90 days, respectively, for non-oncological causes. 30- and 90-day readmission rates were 13% and 19%, respectively. The rate of readmission within 30 and 90 days was 13% versus 19%, with cardiopulmonary complications being the most common cause. In retrospective studies [5-8], the 30-day complication and mortality rates for total lung resection were 30% and 5%-8%, compared with 4%-10% and 0%-3% for lobectomy. In addition, the 90-day mortality rate after total lung resection can be 1-2 times higher than the 30-day mortality rate [9-10]. A controlled study published in the Annals of Surgery in 2022 [11] compared postoperative

complications and mortality rates between pneumonectomy and lobectomy by propensity score matching, and showed that the complication rates of grade III or higher and mortality at 90 days were significantly higher in the group of pneumonectomy than lobectomy (21% vs. 13% and 6.9% vs. 1.9%, respectively). The three complications with the highest rates were hypoxic respiratory failure, bronchopleural fistula, and intrathoracic hemorrhage. In addition, cardiovascular complications were significantly higher in the pneumonectomy group.

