Marc Riquet's team [12] retrospectively analyzed the 10-year survival of 1466 patients undergoing pneumonectomy, and the 5-year and 10-year survival rates were 32% and 19%, respectively. In the analysis of risk factors affecting long-term survival, the investigators found that patients' general physical status and tumor biology were closely related to prognosis, and that the occurrence of nonfatal postoperative complications independently increased the long-term risk of death, which was considered to be indicative of the fragility of patients' general physical status. The investigators compared the long-term survival of patients in the lobectomy versus pneumonectomy groups using propensity score analysis. Cumulative nonneoplastic mortality at 2 years was twice as high in the pneumonectomy group as in the lobectomy group (21% versus 11%), and cumulative nonneoplastic mortality at 5 years was 24% versus 13% in the pneumonectomy group and 2% in the lobectomy group, with the risk of nonneoplastic death increasing by 9% in pneumonectomy group versus 2% in lobectomy group over the postoperative period. The risk of non-tumor death increased by 9% in the total pneumonectomy group and by 2% in the lobular group at 1-2 years. The most common causes of death in both groups were pneumonia and myocardial infarction, both of which were significantly higher in the pneumonectomy group. These non-oncologic deaths are attributable to the impaired general health status of patients after pneumonectomy. A prospective controlled cohort study by Ulrik Sartipy's team [13] found that patients in the pneumonectomy group had a more pronounced decrease in strength scores than those in the lobectomy group (-32% vs. -17%). Recovery from this decline in strength scores was different between the two groups, with Bram Balduyck's team [14] finding that strength scores in patients who underwent lobectomy returned to baseline levels within 1 month after surgery, which supports the idea that adjuvant therapy is often initiated in the first month after surgery, whereas in patients who underwent pneumonectomy, strength scores did not return to baseline levels after 1 year of follow-up. The physical strength scores did not return to baseline after 1 year of follow-up. Patients with pneumonectomy were more likely to have dyspnea, pain, and shoulder dyskinesia than those with lobectomy. Because of the decline in general physical status and strength scores, a significant proportion of patients undergoing pneumonectomy did not receive postoperative adjuvant therapy. In the study by Filippo Lococ's team [15], nearly half of the patients did not receive postoperative adjuvant therapy, although the benefit of postoperative adjuvant chemotherapy on long-term survival has been demonstrated in clinical studies [16]. Recent advances in neoadjuvant/adjuvant combination of immuno- and chemotherapy [17] have

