### **2.4.2 Known Potential Benefits**

Narrowing surgical resection in cases that do well on neoadjuvant or induced chemoimmunotherapy preserves lung function, potentially reducing the risk of perioperative complications, and death. It protects the patient's general state of health, reduces the incidence of long-term non-tumor deaths, maintains a high physical strength score, facilitates adjuvant therapy follow-up, and may result in a long-term survival benefit for the patient.

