### **2.4.2 Assessment of potential risks/benefits**

It has been shown in retrospective studies that total pneumonectomy is only performed when lobectomy is difficult to achieve R0 resection and is associated with higher perioperative complications and mortality than lobectomy, with a significant impact on the patient's general state of health and strength scores, which may contribute to impaired long-term survival. In patients who do well on neoadjuvant or induction therapy, conversion to lobectomy can potentially reduce the incidence of perioperative adverse events, reduce the risk of immediate and long-term non-tumor death, protect the patient's general health and strength scores, and increase the patient's chances of receiving postoperative adjuvant therapy, thereby reducing the risk of tumor-related death.

Risk-minimizing measures: Select patients with good results of neoadjuvant or induction therapy according to strict admission criteria, review the tracheoscopic biopsy before surgery to clarify the status of the bronchus to be preserved, take frozen pathology to clarify the status of the nearest incision margins during the surgery to decide the actual surgical method, and maintain adjuvant therapy after the surgery to minimize the possibility of increasing the risk of local recurrence. Postoperatively, the patient's vital signs, drainage, and air leakage were closely observed to ensure perioperative safety.

Preoperative and intraoperative reassessment

1 Bronchoscopic biopsy of bronchial mucosa to be preserved/EBUS to assess the condition of the outer wall of the preserved bronchus.

2 In cases of main pulmonary artery invasion prior to neoadjuvant therapy, intraoperative

freezing is performed to assess the status of the arterial wall at the site of original invasion.

3 For cases with transverse fissure invasion, pulmonary fissure margins were frozen for pathologic evaluation.

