#### Secondary study endpoints

- Overall survival (OS, unit:month)
- Disease-free survival (DFS, unit: month)
- Surgical Evaluation Indicators.
  - Surgical time (unit: minutes), intraoperative bleeding (unit: ml), intraoperative blood transfusion (unit: ml)
  - Incidence of intraoperative accidents
  - Lymph node dissection: total number of lymph node dissection (unit: one), number of lymph node dissection stations (intrapulmonary,hilar and ipsilateral

mediastinal lymph nodes), and the number of lymph nodes cleared at each station (unit: one).

- Perioperative, 30-day, 90-day complication rates, mortality rates
- Quality of Survival and Pulmonary Function Evaluation at Admission, Discharge, 30 Days, and 90 Days
  - Quality of Life Score: Scored using the short form-36 (SF-36) and recorded on a 100-point scale.
  - Resting oxygen saturation (unit: percentage)
  - Lung function: Tidal volume, Vital capacity, Forced vital capacity, first second vital capacity.
  - Tidal volume, Vital capacity, Forced Expiratory Volume In 1s, all in ml.

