#### Secondary endpoints

Disease-free survival time (in months): Disease-free survival curves were plotted using the Kaplan-Meier method; differences in the risk of disease-free survival between the two groups were assessed using the Log-Rank test with 95% confidence intervals; multivariate analyses were performed using the Cox proportional risk model to assess the effect of subgrouping factors (surgical procedure) and other prognostic factors on the risk of disease-free survival, with 95% confidence intervals for each factor. A multivariate analysis using the Cox proportional risk model was performed to assess the effect of grouping factors (surgical modality) and other prognostic factors on the risk of disease-free survival with 95% confidence intervals for each factor.

- Surgical evaluation indicators.
- Surgical time (unit: minutes), intraoperative bleeding (unit: ml), intraoperative blood transfusion (unit: ml): all quantitative data not conforming to normal distribution, calculate the median, 25% quartile, 75% quartile, the minimum value, the maximum value, and analyze the difference between the two groups by using the rank sum test.
- Incidence of intraoperative accidents: count data, using chi-square test to analyze the difference between the two groups.
- Lymph node dissection: the total number of lymph node dissection (unit: one) and the number of lymph node dissection at each station (unit: one) were non-normally distributed measurements, and the difference between the two groups was analyzed using the rank-sum test; the number of stations of lymph node dissection (intrapulmonary, hilar, and ipsilateral mediastinal lymph nodes) was count data, and the difference between the two groups was analyzed using the chi-square test. Differences between the two groups were analyzed using the chi-square test.
- Tumor R0 resection rate: count data, using the chi-square test to analyze the difference between the two groups.
- Perioperative, 30-day, and 90-day complication rates, and mortality rates: were count data, and differences between the two groups were analyzed using the chi-square test.
- Quality of Survival and Cardiorespiratory Function Evaluation at Admission, Discharge, 30 Days, and 90 Days
- Quality of Life Score SF-36 Scale: Percentage, as a non-normally distributed measure, use rank sum test to analyze the difference between the two groups.

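### The 3-year disease-free survival rate is defined by recurrence and metastasis only; death is never counted as an event, so the rate can be overstated

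*Protocol*

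**What the plan says.** Section 9.1 of the protocol defines two long-term rates side by side. Item 5 is the "disease-free survival rate: defined as the proportion of patients without tumor recurrence or metastasis 3 years after surgery, evaluated by postoperative follow-up". Item 6 is the "3-year overall survival rate: defined as the proportion of patients who are still alive 3 years after surgery". Vital status appears only in item 6.

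The other mentions of DFS give no event rule:

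- The abstract (1.1, Study interventions) lists DFS time, together with a 3-year event-free survival rate that is not defined.
- Section 5.2 lists DFS with its unit, months.
- Sections 10.1 and 10.2 plan Kaplan-Meier curves, a log-rank test and a Cox model. In 10.2, "differences in the risk of disease-free survival between the two groups were assessed using the Log-Rank test", with surgical procedure as the grouping factor. Neither section says whether a death without recurrence is an event, a censoring or a competing event.

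A 3-year rate and a time in months are compatible, so no conflict between 9.1 and sections 5.2 or 10.2 is claimed.

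**The concern.** Taken literally, item 5 counts a patient who dies of pneumonia in the first year, without recurrence, as a patient without recurrence or metastasis, and so as a DFS success. The closing reference to follow-up does not settle the matter, because a patient who died earlier cannot be assessed at 3 years.

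Non-tumour death is central to this trial's rationale. Section 2.4.2 on benefits says that the smaller resection "reduces the incidence of long-term non-tumor deaths". The risk/benefit assessment that follows says conversion to lobectomy can "reduce the risk of immediate and long-term non-tumor death". Item 5 leaves out exactly these events. By the protocol's own background they are about twice as frequent after pneumonectomy as after lobectomy, and section 7.1.1 allows both operations. The omission would therefore raise the pneumonectomy figure more, and a DFS comparison by procedure could understate a real difference.

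**Working it through.** The protocol states no expected DFS rate, event count or power, and section 5.3 says the 50 patients were not derived from a hypothesis test. There is no figure to reproduce; the check is of direction and possible size.

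**Inputs**

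- Non-neoplastic mortality *d* = 0.11 (lobectomy) and 0.21 (pneumonectomy): the 2-year figures in section 2.2, taken unchanged at 3 years (assumption).
- Recurrence by 3 years *r* = 0.30 to 0.50: an assumption; the protocol gives none.
- 90-day mortality of 1.9% and 6.9% (section 2.2), as a lower variant.

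**Model 1**, independent constant hazards, with *d* and *r* the risks each cause would give alone:

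- λr = -ln(1-r)/3 and λd = -ln(1-d)/3
- DFS counting death: S = (1-r)(1-d)
- Death without recurrence: D = λd/(λr+λd) × (1-S)
- Overstatement: scored disease-free, D; censored, (1-r) - S = d(1-r); dropped from the denominator, S/(1-D) - S

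**Model 2**, with *d* and *r* the observed cumulative incidences, so that every non-neoplastic death occurs without earlier recurrence:

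- S = 1 - r - d
- Overstatement: scored, d; censored, S^(r/(r+d)) - S; dropped, S/(1-d) - S

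**Worked case**, lobectomy with r = 0.30:

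- Model 1: S = 0.70 × 0.89 = 0.623 and D = 0.093. Scored +9.3 points; censored 0.700 - 0.623 = +7.7; dropped 0.623/0.907 - 0.623 = +6.4.
- Model 2: S = 0.59. Scored +11.0; censored 0.59^(0.30/0.41) - 0.59 = +9.0; dropped 0.59/0.89 - 0.59 = +7.3.

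**Overstatement in percentage points for r = 0.30 to 0.50**

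| How the dead are handled | Lobectomy, model 1 | Lobectomy, model 2 | Pneumonectomy, model 1 | Pneumonectomy, model 2 |
|---|---|---|---|---|
| Scored disease-free | 8.0-9.3 | 11.0 | 15.4-17.8 | 21.0 |
| Censored | 5.5-7.7 | 7.2-9.0 | 10.5-14.7 | 12.8-16.7 |
| Dropped | 3.9-6.4 | 4.8-7.3 | 7.2-12.0 | 7.7-13.0 |

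**Effect on the comparison by procedure**, with equal recurrence. When death counts, lobectomy leads by (1-r)(0.21-0.11) = 5.0-7.0 points in model 1 and by 10.0 in model 2. The loss of that lead is the pneumonectomy overstatement minus the lobectomy overstatement at the same r:

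- scored: 7.4-8.5 (model 1) and 10.0 (model 2)
- censored: 5.0-7.0 and 5.6-7.8
- dropped: 3.3-5.6 and 2.9-5.7

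Whether the lead shrinks, vanishes or changes sign depends on the model, so no reversal is claimed.

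**90-day mortality only** (model 2, d = 0.019 and 0.069, none of these deaths after a recurrence): 0.9-1.9 points after lobectomy and 3.2-6.9 after pneumonectomy.

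**Precision for scale.** The 95% half-width for one rate near 50% in 50 patients is 1.96 × √(0.25/50) = 13.9 points. For a difference with an assumed 25/25 split it is 1.96 × √(2 × 0.25/25) = 27.7 points.

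**The case against.** The best defence is that item 5 is ambiguous rather than wrong. The endpoint is called survival, and a status assessed at 3 years by follow-up may be taken to describe a living patient; on that reading there is no bias. The contrast with item 6 is not decisive, since a definition of overall survival has to mention being alive. This reading is fair, but the text does not state it, and the other readings all err in the same direction. Of those, dropping the dead has the least support in the wording.

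A second argument is that event and censoring rules are commonly left to an SAP, which may exist. That covers the silence of 5.2 and 10.2. It does not cover item 5, which fixes a definition that omits death. It does make the effect on the section 10.2 comparison conditional: it arises only if item 5's event is carried into the time-to-event analysis.

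Third, the size rests on borrowed inputs. The mortality comes from other surgical series, while section 6.1 selects patients under 75, ASA I-III, with adequate cardiopulmonary function. Recurrence is assumed, and the 11- and 21-point ceilings need every non-neoplastic death to precede any recurrence. All of this stands and limits the size, not the direction.

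Finally, DFS is secondary, the R0 primary endpoint is untouched, and overall survival and the 30- and 90-day mortality rates still show these deaths. That also stands.

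**Conclusion.** The concern holds. The protocol's one explicit DFS definition counts recurrence and metastasis only, and nothing elsewhere adds death. Unless the unstated reading of alive and recurrence-free is applied, the 3-year DFS rate is overstated.

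On the illustrative inputs the excess is about 4-11 points after lobectomy and 7-21 after pneumonectomy; on 90-day mortality alone it is about 1-2 and 3-7. A DFS advantage of 5-10 points for lobectomy would lose about 3-10 points. The direction does not depend on the assumed recurrence; the size does, and it also depends on applying the background mortality to this population.

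The harm is limited. Against half-widths of about 14 points for one rate and 28 for a difference, the distortion would rarely decide a test. It would, however, centre the interval on the wrong value, and the 3-year DFS rate is one of the main long-term results. The wording should be corrected.

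**What to change.** In section 9.1, item 5, define DFS once as time from surgery to the first of recurrence, metastasis or death from any cause, with patients free of these events censored at last contact. Take the 3-year rate and its 95% confidence interval from the Kaplan-Meier curve planned in 10.2, and refer to this definition in 5.2 and 10.2. Define the abstract's event-free survival rate at the same time, or remove it.

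If a recurrence-only measure is wanted, give it its own name and estimate it as a cumulative incidence with death without recurrence as a competing event.

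The cost is a short wording change. Three years of follow-up (section 8.3) and survival status (section 9.1, item 6) are already planned, so no new data are needed. The reported DFS will be less favourable and, as a composite, will no longer isolate recurrence.

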## 9.2 Safety and other evaluations

The main methods of safety evaluation of the study intervention include.

- 1) Clinical presentation;
- 2) Physical examination;
- 3) Vital signs (e.g., temperature, pulse, blood pressure);
- 4) Routine blood and blood biochemistry tests.

## 9.3 Adverse Events and Serious Adverse Events

### 9.3.1 Definition of Adverse Events (AE)

This refers to all adverse medical events that occur after a subject has undergone radical lung cancer surgery, which may be manifested by signs, symptoms, disease, or abnormal laboratory tests, but are not necessarily causally related to the trial intervention.

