## 5. Research design

### 5.1 Overall design

In this single-arm, open-label, multicenter, prospective clinical trial, 50 cases of operable non-small-cell lung cancer requiring pneumonectomy were proposed to be enrolled. Patients will be treated with neoadjuvant or inductive combination therapy of immuno- and chemo- by evaluation from multidisciplinary discussion (Department of Thoracic Surgery, department of Respiratory Medicine, department of Radiology), than undergo open or minimally invasive radical surgery for lung cancer and systematic lymph node dissection. Peri-operative complications, lymph node dissection, R0 resection rate, and postoperative short-term and long-term efficacy outcomes will be recorded and evaluated.

Participating centers:

- 1 Ruijin Hospital, Shanghai Jiao Tong University School of Medicine, Shanghai, China
- 2 Shanghai General Hospital of Shanghai Jiao Tong University School of Medicine
- 3 The Ninth People's Hospital of Shanghai Jiao Tong University School of Medicine
- 4 Huadong Hospital, Fudan University Medical College, Shanghai, China

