## **7. Research interventions**

### **7.1 Giving the research intervention**

#### **7.1.1 Description of the research intervention**

After the patients were enrolled in the group, further relevant examinations (bronchoscopy, chest enhanced CT, PET-CT (optional), cranial MR, cardiac ultrasound, pulmonary function, electrocardiogram, and blood test) were completed, contraindications to surgery were ruled out, and they were evaluated to receive neoadjuvant/induced chemo-immunotherapy after multidisciplinary discussion (thoracic surgery, respiratory medicine, pathology). After completion of treatment, the patient is reassessed and discussed multidisciplinary for surgical feasibility. Open or minimally invasive (thoracoscopic-assisted, robotic-assisted) radical lung cancer surgery with systemic lymph node dissection is performed, including

pneumonectomy, lobectomy, combined lobectomy, and sleeve lobectomy (with or without pulmonary angioplasty/sleeve). Based on the surgical pathology and guidelines, the postoperative adjuvant treatment and follow-up plan was individualized after multidisciplinary discussion.

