### 9.3.2 Definition of Serious Adverse Event (SAE)

means an adverse medical event resulting in death, life-threatening, permanent or serious disability or loss of function, the need for hospitalization of the subject, or prolonged hospitalization after the subject has undergone radical lung cancer surgery. A serious adverse event (SAE) is defined as an adverse medical event resulting in death, life-threatening, permanent or serious disability or loss of function, hospitalization or prolonged hospitalization after radical lung cancer surgery.

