### **9.3.4 Timing, frequency, follow-up and regression of adverse event assessment**

Time and frequency of adverse event assessment: assessed every three days during hospitalization, and once at each follow-up visit after discharge.

Follow-up of adverse events: The investigator should follow up the adverse events; observe the final regression until the symptoms disappear or stabilize; the investigator should follow up the results with the principal investigator and the ethics committee.

All adverse events should be collected on a case report form (CRF), which should include a description of the event, time of occurrence, physician's assessment of severity, relationship to the study intervention, and time to resolution/stabilization of the event.

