### **9.3.6 Reporting of Serious Adverse Events**

Serious adverse events should be promptly documented on a Case Report Form (CRF) and reported within 24 hours to the Principal Investigator, Ethics Committee.

- 1) the description of the adverse event;
- 2) time of occurrence and duration;
- 3) whether the adverse event was serious or unintended;
- 4) mode of onset;
- 5) assessment of severity;
- 6) regression;

7)Measures taken in response to the adverse event.

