### 10.3 Safety analysis

Adverse events were coded, calculated, and expressed using severity, frequency, and association with intervention. Adverse events leading to Adverse events leading to discontinuation of the study intervention should be listed separately from serious adverse events arising from the treatment.

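### The adverse event window opens only after surgery, so pre-operative events in consented patients are not adverse events, and their serious-event status is unclear

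*Protocol*

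**What the plan says.** **Definitions.** Section 9.3.1 on adverse events: "This refers to all adverse medical events that occur after a subject has undergone radical lung cancer surgery". The same sentence adds "but are not necessarily causally related to the trial intervention". Section 9.3.2 lists the seriousness criteria and ends its first sentence with "prolonged hospitalization after the subject has undergone radical lung cancer surgery". Its second sentence repeats the list with a similar closing phrase.

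**Assessment, reporting and analysis.** Section 9.3.4: "Time and frequency of adverse event assessment: assessed every three days during hospitalization, and once at each follow-up visit after discharge". Section 9.3.6 requires serious events to be "reported within 24 hours to the Principal Investigator, Ethics Committee". Section 10.3: "Adverse events were coded, calculated, and expressed using severity, frequency, and association with intervention". It also asks for a separate listing of adverse events that cause the intervention to be stopped.

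**Sequence.** Section 5.1, having described enrolment of 50 cases, continues: "Patients will be treated with neoadjuvant or inductive combination therapy of immuno- and chemo- by evaluation from multidisciplinary discussion", with surgery afterwards. Section 7.1.1, headed as the description of the research intervention, opens "After the patients were enrolled in the group, further relevant examinations" and then goes through chemoimmunotherapy, reassessment and surgery. Section 6.3 has patients sign consent once they are found eligible, and the section 7.5 schedule puts consent in the screening column.

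**The concern.** The definition excludes events by timing alone. Section 9.3.1 requires no causal link, so it makes no difference whether a pre-operative event comes from the drugs, the disease or the work-up. If enrolment precedes induction, a consented patient who has a serious reaction and never reaches surgery contributes nothing to the adverse event data. The safety tables would then describe only patients who got as far as the operation, with nothing to show that others had been left out.

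Expedited reporting is also at stake. The 24-hour duty depends on an event being a serious adverse event, and for a pre-operative death or hospitalization that turns on how one trailing phrase is parsed. Two centres could report the same event differently and each be following the protocol.

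**Working it through.** No formula applies and the protocol states no figure to reproduce, so the check sets the sections side by side.

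**1. Does any section widen the 9.3.1 window?**
- Section 9.3.4 covers hospital stays and follow-up visits. A hospital stay could be pre-operative, but nothing found then meets the 9.3.1 definition.
- The 7.5 schedule has 1 screening + 1 peri-operative + 8 follow-up = 10 columns, none named for induction. This also fits enrolment after induction, so it decides nothing about timing.
- Section 8.1 treats serious reactions as grounds for stopping the intervention, and 8.2 puts the reason for withdrawal on the case report form. Neither makes the event an adverse event report with grading, attribution and follow-up.

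No section widens the window.

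**2. Does 10.3 fit the window?** Section 10.3 wants adverse events that stop the intervention listed separately. An event that halts induction or prevents the operation is an obvious candidate, yet 9.3.1 says it is not an adverse event. If only surgery counts as the intervention, a window that opens after surgery leaves that listing little to hold.

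**3. What does 9.3.2 exclude?** The closing phrase about surgery has three possible readings:
- it limits only prolonged hospitalization, which the comma in the first sentence allows;
- it limits all hospitalization, which is natural in the second sentence, where the comma is absent;
- it limits every criterion, including death.

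The text does not settle which is meant, so reporting under 9.3.6 is uncertain for pre-operative events.

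**4. What is captured elsewhere?** Intraoperative accidents and perioperative complications are endpoints (5.2, 9.1), and 7.5 has perioperative complications recorded by treating staff. For events during the operation, mainly the adverse event classification is affected. No endpoint captures events during induction.

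**5. When does enrolment happen?**

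| Points to before induction | Can be read as during or after induction |
|---|---|
| 1.1, Study population: lists chemoimmunotherapy as something the patient may need | 1.1, Study interventions: goes from enrolment and work-up to surgery, with no induction between |
| 5.1: treatment follows enrolment | 2.4.2, Assessment of potential risks/benefits: selects patients who responded well |
| 7.1.1: enrolment, work-up, then chemoimmunotherapy | 6.1, criterion 3: describes patients as receiving the therapy |
| | 7.5: moves from screening to the peri-operative period |

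Section 6.2, criterion 4 is left out because it concerns only radiotherapy and targeted therapy. The study-interventions figure is not shown in the text available, and it could bear on the sequence.

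**6. Size.** Consent comes before surgery under either reading. All 50 planned patients who reach surgery therefore have an interval outside 9.3.1, and a patient who is never operated on has no window. The protocol gives neither the interval's length nor an event rate.

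**The case against.** The strongest reply is that this is a surgical study. Section 7.1.2 says no drug trial is involved, 5.3 calls the study observational, and the listed risks in 2.4.1 are surgical. The safety aim in the abstract and at the end of 2.2 concerns converting from pneumonectomy to lobectomy. A window anchored on surgery matches that aim. Part of this stands: a reader might infer that a drug-safety objective has failed, but the protocol states no such objective. It does not remove the gap. Section 7.1.1 includes the chemoimmunotherapy in the intervention, 9.3.1 disregards cause, and even a purely surgical reading leaves out the operation and the time from consent to it.

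Three other stronger readings are tempting and also unsupported:
- **That 9.3.2 definitely excludes pre-operative hospitalization or death.** The wording is ambiguous; the text supports only that their status is unclear.
- **That intraoperative events go unrecorded.** They are collected as endpoints.
- **That enrolment certainly precedes induction.** Sections 5.1 and 7.1.1 say so, but other text can be read differently, and under later enrolment the gap is shorter.

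It is also fair to say that withdrawal reasons on the case report form leave some trace of events that prevent surgery. That trace is not a graded event or a 24-hour report. Nor is this a matter for the analysis plan: the protocol itself fixes the definitions and the reporting duty.

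**Conclusion.** The point holds as a should-fix. Taken literally, 9.3.1 keeps pre-operative events in consented patients out of the adverse event data and out of 10.3, while 9.3.2 and 9.3.6 leave expedited reporting of such events uncertain. The harm is incomplete safety reporting for consented patients. The R0 endpoint is not affected.

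The size depends on enrolment timing. If 5.1 and 7.1.1 govern, the gap covers the whole induction period, reassessment and the operation, and it includes patients who never reach surgery. If enrolment follows induction, it covers only consent to the end of surgery, and 5.1 and 7.1.1 need correcting. Both readings assume that consent is signed before surgery, as 6.3 and 7.5 indicate. No event count is claimed.

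**What to change.** 1. Reconcile enrolment timing across the abstract (Study population and Study interventions), 2.4.2 (Assessment of potential risks/benefits), 5.1, 6.1 criterion 3, 7.1.1 and 7.5.
2. In 9.3.1 and 9.3.2, start the adverse event and serious adverse event window at signed informed consent. State that it includes the operation and any induction given after consent, and that it applies to every seriousness criterion. This wording works under either enrolment reading.
3. If enrolment precedes induction, add adverse event recording for that period to 9.3.4 and 7.5 on the existing case report form, and report those events in 10.3.

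The cost is a wording amendment and modest extra event recording and serious-event reporting before surgery. The protocol does not describe induction visits, so the workload cannot be sized from it. No extra patients and no change to the endpoints are needed.
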